**Table E2. Defining receipt of guideline-based medications**

Condition	Classification	Guideline for minimal medications
COPD	Prior to 2024	
	Class A	Rescue inhaler: Short acting beta agonist (SABA)
	Class B	Rescue: SABA AND Controller: Long-acting beta agonist (LABA) OR Long-acting muscarinic agent (LAMA)
	Class C	Rescue: SABA AND Controller: Long-acting muscarinic agent (LAMA)
	Class D	Rescue: Short acting beta agonist AND Controller: Long-acting muscarinic agent (LAMA) OR LAMA + LABA OR ICS + LABA
	After 2024:	
	Class B	Rescue: SABA AND Controller: LAMA AND LABA
	Class E (formerly C/D)	Rescue: SABA AND Controller: LABA AND LAMA

Asthma	Steps 1-2 (formerly intermittent or mild persistent asthma)	SMART Therapy: Inhaled corticosteroid (ICS) + LABA as needed OR Rescue: ICS + SABA together
	Step 3 (formerly moderate persistent asthma)	SMART Therapy with low dose ICS + LABA
	Steps 4 – 5 (formerly severe persistent asthma)	SMART Therapy with moderate dose ICS for persistent asthma)

Pre-specified secondary outcomes included the proportion of patients in each arm who received chronic lung disease education, defined as referral to any class or one-on-one education on chronic lung conditions or patient-reported receipt of education on identifying and responding to signs of exacerbations, staying active, or breathing training. In addition, we measured several patient-reported outcomes, including disease-specific quality of life, as measured by the St. George Respiratory Questionnaire (SGRQ) and symptoms, as measured by the symptom subscale of the SGRQ. Patient-reported quality of care was measured using the short form of the Patient Assessment of Chronic Illness Care (PACIC) (mean item score 1-8). Self-reported adherence to inhaler therapy was defined as the proportion of patients taking all doses of controller medications as prescribed in at least five of the last seven days. For the intervention arm, provider acceptance of recommended care was defined as the proportion of PSNP recommendations for which the provider took action, including placing of referrals, orders for new prescriptions, or approval for the health coach to follow up.

Additional outcomes not pre-specified in ClinicalTrials.gov included exacerbations and utilization of acute and primary care services were identified through the electronic medical records from participating clinics, the county hospital, and outside facilities for ED visits and hospitalizations that were viewable through the Care Everywhere feature in Epic. A study physician (MK) blinded to study arm reviewed cases to identify exacerbations with blinded consultation from the study pulmonologist (GS) as needed.

### Analysis Methods

We summarize by arm the demographic and clinical characteristics of participants in the PushCon study using descriptive statistics but, following convention, do not compare characteristics between arms using statistical tests. To examine differential dropout by arm, affecting Week-16 survey outcomes only, we compare characteristics of participants with and without missing outcomes using chi-square or Wilcoxon rank-sum tests.

To analyze study outcomes, we used generalized estimating equation (GEE) models to estimate the mean (95% CI) ratio of arm-specific rates (for binomial or count outcomes) or geometric means (for continuous outcomes) and to generate 2-sided p-values, while accounting for correlated outcomes within study clinics. For longitudinal outcomes, assessed at baseline (after consent but before randomization; Week 0) and at the end of the intervention period (Week 16), we fit time and time\*arm as fixed effects, and nest correlated outcomes within study clinics; for cross-sectional outcomes we exclude the time effect from the model. In the setting of RCTs, the constrained longitudinal data analysis (cLDA) approach, used here, estimates a common mean across arms at baseline; in contrast, the LDA approach would include a fixed effect for arm to estimate distinct mean outcomes at baseline. The cLDA model is equivalent to the ANCOVA model when no data are missing; however, participants with some missing values, for example, at follow-up only, contribute to the cLDA model but not the ANCOVA model, increasing the cLDA's relative power.

*Receipt of guideline-recommended care* was calculated as a single proportion that can be modeled cross-sectionally. Each participant's outcome arises from a ratio of two counts,  $p_{care} = x/d$ , where  $d$  is the number of gaps in care noted over the 12-month pre-baseline (denominator, see Appendix A), and  $x$  is the number of these gaps that were noted as addressed during the 16-week intervention (numerator). To estimate the rate ratio (RR) (95% CI) we modeled  $x$  as a function of arm, specified a negative binomial distribution for  $x$  and used a log link with  $\log(d)$  as an offset.

*Receipt of all guideline-recommended medications* is a binary longitudinal outcome. All medications recommended by GOLD/GINA guidelines for each participant were identified prior to the start of the study. The outcomes at Week 0 (using EHR data the 12 months prior to randomization) and at Week 16 (using EHR data from the 16-week intervention period) are scored  $y=1$ , if all were prescribed, and  $y=0$ , otherwise. Using a constrained longitudinal data analysis (cLDA) approach, which estimates equal rates by arm at baseline, we modeled  $y$  as a function of time and the time\*arm interaction, specified that  $y$  is binomial, and used a log link to estimate RRs at Week 16. Other binomial outcomes modeled analogously.

The *Saint George Respiratory Questionnaire*, a patient-reported outcome, is also measured longitudinally. It consists of 51 items in three domains: symptoms, activity, and impact, and has a total **score** ranging from 0 to 100, with higher scores indicating greater disability. The analysis method is the same for the overall score and its domains. Using the cLDA approach, we modeled  $z$  as a function of time and time\*arm, used a log link, and specified that  $y$  has a negative binomial distribution. The model estimates geometric means (95% CI) and estimates the relative mean (RM) (95% CI) to compare the HC and UC arms at Week 16. Another outcome using this model is *PACIC*.

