### **Setting**

The PuSHCon study was conducted between October 2020 and January 2025 at ten urban Federally Qualified Health Centers (FQHCs) or “FQHC look-alikes” by the Health Services Resources and Services Administration. Eight participating study clinics were in the community and two were located at the county hospital medical campus.

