### **Recruitment, enrollment, and randomization within clinics**

Potentially eligible patients were identified primarily through review of electronic medical records (EMR) from the previous 12 months for the 10 clinics and the county hospital and emergency department (ED). Patients with a COPD- or asthma-related diagnosis (ICD-10 parent codes J41 – J45) were assessed by review of electronic health records and their primary care provider (Figure 1). A research assistant (RA) attempted to contact the patients not excluded by telephone and mail to describe the study and conduct additional eligibility screening. Eligible patients interested in the study met with the RA remotely or at their primary care clinic for informed consent and study enrollment. Within each clinic, patients were randomized 1:1 to HC or UC, in blocks of 10, using a random generator (Microsoft Excel 360). Randomization by the individual, rather than by

clinic, was chosen when a pilot phase of the study found a higher ICC than anticipated, such that clinic-level randomization would require a sample size nearly 80% larger than individual-level randomization. In addition, individual level randomization enhanced recruitment of clinics by enabling the study team to offer coaching for some patients at each participating clinic. After obtaining baseline survey measurements, the RA activated a lookup feature to reveal the participant's study arm assignment.

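### The between-arm GEE models rest on ten clinics, with no variance estimator, small-sample correction or reference distribution stated; an uncorrected clinic sandwich with z would be anti-conservative

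*Combined protocol and SAP*

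**What the plan says.** Under Analysis Methods, "we used generalized estimating equation (GEE) models to estimate the mean (95% CI) ratio of arm-specific rates" or of geometric means, with two-sided p-values, "while accounting for correlated outcomes within study clinics". Longitudinal models include time and time-by-arm effects and "nest correlated outcomes within study clinics".

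The two primary outcomes are specified further:
- **Care gaps:** a cross-sectional negative binomial model with log link and log(d) offset.
- **Medications:** a binomial constrained longitudinal model that "used a log link to estimate RRs at Week 16".

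The Setting section reports ten clinics: "Eight participating study clinics were in the community and two were located at the county hospital medical campus". On allocation, the recruitment section says: "Within each clinic, patients were randomized 1:1 to HC or UC, in blocks of 10". It also says that "a pilot phase of the study found a higher ICC than anticipated", without giving the value.

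Distributions, links, offset and fixed effects are all given. Working correlation, variance estimator (robust or model-based), small-sample correction and reference distribution (z or t, with df) are not.

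**The concern.** The ordinary way to carry out a clinic-clustered GEE is a robust sandwich SE with a normal reference. That sandwich is justified as the number of clusters grows, and here there are ten. It is biased downward with few clusters, and the z reference ignores that the variance is estimated from ten contributions. Both errors make intervals too narrow.

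Randomizing individuals within clinic does not cure this, because a clinic-level sandwich still builds its variance from ten clinic totals.

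At stake is the inference on the care-gap outcome and, if clinic is also the cluster in the longitudinal models, on medications, SGRQ and PACIC. Provider acceptance (one arm only) and the dropout comparisons are not affected.

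**Working it through.** The plan gives no figure to reproduce on this point: it states no alpha, sample size or ICC value. A two-sided 5% level is inferred from the 95% CIs.

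**Inputs from the documents.** K = 10 clinics (Setting); 1:1 allocation within clinic in blocks of 10 (recruitment section); 165 patients assigned to the coach (HC arm section).

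**Closed form, ten equal clinics balanced by arm.** The arm effect then behaves like a mean of K within-clinic contrasts. The uncorrected sandwich variance is (K−1)/K = 0.9 times the unbiased variance of that mean. The reported z statistic is therefore a t variable on 9 df divided by √0.9.

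1. True error of a nominal 5% test: P(|t₉| > 1.960 × √0.9) = P(|t₉| > 1.859) = 0.096. Coverage is 1 − 0.096 = 90.4%.
2. Nominal p that corresponds to a true 5%: the t₉ critical value is 2.262, so the reported z must reach 2.262/√0.9 = 2.385, which is p = 0.017.
3. Half corrections: t₉ on the uncorrected SE gives P(|t₉| > 2.262 × √0.9) = 0.060. K/(K−1) scaling with z gives P(|t₉| > 1.960) = 0.082.
4. K/(K−1) scaling with t₉: exactly 0.05. CI width ratio to the uncorrected interval, on the log scale: 2.262 × √(10/9) / 1.960 = 1.22.
5. Mancl-DeRouen with t₉: the SE is divided by 0.9, so P(|t₉| > 2.262 × √0.9 / 0.9) = P(|t₉| > 2.385) = 0.041. Width ratio: 2.262 / (1.960 × 0.9) = 1.28.

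These results need no value for the ICC, outcome rate or total N.

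**Simulation under no arm effect.** Assumptions that are not in the documents: N = 330 (2 × 165, from 1:1 allocation); 33 per clinic, or 8–70 per clinic; mean of 5 gaps with 40% closed; medications about 42% at Week 0 and 50% at Week 16; participant SD 0.5 (gaps) and 1.5 (medications) and clinic SD 0.1–0.6 on the logit scale. There were 4,000 runs per care-gap scenario and 2,500 per medication scenario (Monte Carlo SE about 0.35–0.6 points). The arm effect is common to all clinics.

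| Method | Care gaps | Medications |
|---|---|---|
| Clinic sandwich, z, equal clinics | 8.8–10.2% | 9.2–9.9% |
| Clinic sandwich, z, 8–70 per clinic | 10.1–11.4% | 10.2–10.9% |
| Mancl-DeRouen, t₉ | 3.9–5.5% | 3.1–5.4% |
| Model-based SE, estimated scale | 2.4–5.6% | 4.1–5.8% |
| Participant-level robust SE, clinic fixed effects | 4.9–6.2% | not run |
| Participant as GEE cluster | not applicable | 4.4–6.0% |

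The last four rows also include a more extreme assumed split of 5–110 per clinic. A separate simulation (6,000 runs per scenario; cross-sectional binary and count outcomes) gave 9.0–9.8% for the uncorrected sandwich with equal clinics and 10.8–11.7% with 10–80 per clinic. SGRQ and PACIC were not simulated.

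**The case against.** **The plan never says this estimator was used.** That stands. A reader might infer that the trial's p-values and intervals are inflated, or that the true error on the primary outcomes is about 10%. The documents do not support that inference. The figure belongs to one combination of unstated choices, and the table shows other combinations near 5%. The gap can even act in the other direction: a check of the care-gap negative binomial with dispersion 1, fixed scale and model-based SEs rejected in only 0.0–0.1% of null trials.

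**The longitudinal wording is ambiguous.** This stands too. The natural reading of "nest correlated outcomes within study clinics" makes clinic the GEE cluster. If the participant is the cluster and clinic only a nesting level, medications do not have a ten-cluster problem.

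**A clinic-level correction may be the wrong remedy, since patients were randomized individually.** This stands in part, because the ranking of remedies depends on the target. If arm effects vary over a wider population of clinics around a zero mean (assumed logit SD 0.4), participant-level SEs with clinic fixed effects reject 17.0–26.2% of the time on care gaps, and Mancl-DeRouen with t₉ 3.9–6.8%. If the same variation averages to zero over these ten clinics, the participant-level analysis with clinic fixed effects gives 4.5–4.9% and Mancl-DeRouen with t₉ under 1%. So it would be wrong to say that the participant-level option requires an identical effect in every clinic. The documents do not say which target is meant.

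**The unequal clinic sizes are invented.** They are assumptions, since the documents give none. The 9.6% for equal clinics does not depend on them.

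**Conclusion.** The concern holds as an unspecified method with a quantified risk, not as a demonstrated error. It is more than missing detail, because the customary implementation of the stated model gives intervals that are too narrow with ten clinics.

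Under that implementation, true error is about 9.6% for ten equal clinics and about 10–12% with the assumed unequal sizes. With equal clinics, a reported p between about 0.017 and 0.05 would not be significant at a true 5% level. The care-gap outcome is directly exposed; medications and the other longitudinal outcomes are exposed only if clinic is the cluster. Under a common arm effect, the participant-level and estimated-scale model-based analyses show little or no inflation.

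The pilot remark on ICC should not be read as fixing the size of the problem: no ICC value is given, and the closed form does not use one. This should be fixed; confidence is medium, because the result turns on a choice that the documents leave open.

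**What to change.** For each between-arm model, state the cluster unit, working correlation, variance estimator and reference distribution with df. Do not rely on an uncorrected clinic sandwich with z. Say which target is meant, and choose accordingly:

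- **(a) Clinic-level GEE with a small-sample-corrected sandwich and t on 9 df.** This also covers arm effects that vary over a wider population of clinics. With equal clinics, K/(K−1) scaling gives 5% with CIs about 22% wider than the uncorrected ones; Mancl-DeRouen gives about 4% with CIs about 28% wider (28–41% in the care-gap simulations).
- **(b) Participant-level robust SEs with clinic as a fixed effect.** Individual randomization within clinic justifies this, and it targets the average effect in these ten clinics. CIs were about 5–17% wider than uncorrected ones for care gaps. A Poisson working model with robust SEs can replace the log-binomial if that fails to converge with clinic terms.

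The study ended in January 2025, so any choice made now is post hoc. Report the results from the estimator first used beside the corrected ones, and label the corrected ones as added after data collection. The cost is a few sentences of text, a re-run of the between-arm models, and wider intervals with a matching loss of power.

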### Pulmonary-specialist - Health coach Consultation (HC) arm

Patients randomized to the intervention arm continued to have access to all resources available through usual care. In addition, they received a health coach-facilitated consultation and support for 16 weeks, as our protocol previously described. Health coaches first reviewed the EMR and met with the patient to complete the Pulmonary Specialist Consultation Form, a tool to organize patient information for the PSNP. HCs recorded patient medical history and co-morbidities, smoking history, risk and symptom assessment, COPD and asthma medications and treatment history, environmental triggers and screens for symptoms of sleep apnea, from review of the EMR and information supplied by the patient. The HC then presented the patient's information to the PSNP who could gather additional information from the medical record if needed. The PSNP created a set of recommendations for changes in care using the GOLD/GINA guidelines without needing to see the patient.

The health coach was assigned 165 patients over the course of the study with a maximum caseload of 30 patients at any given time. The HC was expected to conduct at least one in-depth consultation with the study PSNP, ideally within the first 2-3 weeks of randomization, and to attend medical visits between the patient and their primary care provider (PCP) throughout the intervention period, whenever possible. Health coaches were expected to meet in person with the participant at least 2 additional times over the course of the study and to conduct a phone check-in call at least every 3 weeks, including within two weeks after each medical visit, resulting in at least 5 points of contact over 16 weeks. Additional contacts were guided by patient needs and preferences. Health coaching focused on helping patients identify and achieve self-care goals for their COPD using techniques from motivational interviewing and adult learning models. Specific content included asthma or COPD education, action planning for exacerbations, practicing optimal inhaler use, and facilitating consultation with a PSNP. The Health Coach documented interactions in a study-specific database.

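### Clinic is the randomization stratum but is used only as a GEE cluster, so ten clinics carry the variance and the primary intervals either under-cover or are wider than necessary

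*Combined protocol and SAP*

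**What the plan says.** The section on recruitment and randomization states: "Within each clinic, patients were randomized 1:1 to HC or UC, in blocks of 10". It explains that individual randomization was chosen because "a pilot phase of the study found a higher ICC than anticipated", so that "clinic-level randomization would require a sample size nearly 80% larger than individual-level randomization". The Setting section places the study "at ten urban Federally Qualified Health Centers".

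Under Analysis Methods, all outcomes are analysed by GEE "while accounting for correlated outcomes within study clinics". Longitudinal outcomes have time and time-by-arm terms "as fixed effects, and nest correlated outcomes within study clinics". For the first primary outcome, the number of care gaps closed is modelled "as a function of arm, specified a negative binomial distribution for" that count, with a log link and the log number of gaps as offset. For the second primary outcome (all recommended medications), the model is binomial with a log link and has time and time-by-arm terms only. Neither mean model has a clinic term.

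The section does not state the working correlation, the standard-error type, any small-sample correction, the degrees of freedom, or whether inference is to these clinics or to a wider population of clinics.

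**The concern.** Arms are compared within clinics, between patients who were each randomized. The analysis should follow that structure, with clinic as a stratum and the participant as the independent unit. Clustering on clinic instead makes each clinic one independent contribution to the variance, so the standard error of both primary outcomes rests on ten terms.

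A GEE sandwich from ten clusters tends to be too small. Used with normal critical values, it gives intervals that are too short. Corrected and referred to t(9), it is valid but pays for having few clusters, a price the design did not need to incur. The trial moved to individual randomization to avoid the cost of clinic-level inference, and the analysis gives part of that saving back. At stake are the confidence interval and p-value of both primary outcomes.

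**Working it through.** **Inputs from the document.** Ten clinics; 1:1 allocation in blocks of 10 within clinic; "The health coach was assigned 165 patients over the course of the study"; two-sided p-values with 95% intervals; the 80% inflation figure.

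**Assumptions.** Total N = 330 (2 × 165) and 33 per clinic (330/10) follow from 1:1 allocation; neither is stated. Clinic sizes, event rates and effect sizes are also assumed.

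**1. The plan's own figure.** The 80% cannot be reproduced, because neither the ICC nor the clinic size is given. It can be inverted through the design effect 1 + (m − 1) × ICC = 1.8:
- m = 33: ICC = 0.8/32 = 0.025
- m = 20: 0.8/19 = 0.042
- m = 50: 0.8/49 = 0.016

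**2. Does omitting clinic from the mean model cost efficiency?** Hardly. Ignoring clinic altogether would inflate the standard error by 1/√(1 − ICC): 1/√0.975 = 1.013 at ICC 0.025 and 1/√0.958 = 1.022 at 0.042. Because arms are balanced within clinics, the estimator barely changes. The simulated SD of the log relative rate without and with clinic was 0.0925 and 0.0927 (care gaps) and 0.1051 and 0.1050 (medications). The largest difference in any scenario was about 1.5%. Adding clinic while still clustering on clinic left the mean robust standard error at 0.0779 versus 0.0781 (care gaps, unequal clinics).

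**3. Where the cost arises.** In that last setting the uncorrected clinic-level standard error averaged 0.0779 against a true SD of 0.0862, a ratio of 0.90. Clinic fixed effects with participant-level errors gave 0.0853 against 0.0854.
- *Uncorrected, normal critical value.* If ten clusters shrink the standard error by √(9/10), the effective threshold is 1.96 × 0.949 = 1.859, and P(|t(9)| > 1.859) = 0.096. Simulated type I error was 0.095 to 0.110.
- *Corrected, t(9).* The critical value alone widens the interval by 2.262/1.960 = 1.154. A test with 80% power under the normal distribution has about 70% under t(9).

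**4. Simulation, one binary Week-16 outcome.** N = 330, clinics of 10 to 60, blocks of 10, usual-care rate 40%, relative rate 1.35, constant effect, 3,000 runs per setting. Values are for ICC 0.025 / 0.08. Two sets of runs are shown, each with its own comparator.

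| Analysis | Coverage | Power | Median width (log scale) |
|---|---|---|---|
| Set 1: clinic cluster, small-sample correction, t(9) | 0.945 / 0.951 | 0.642 / 0.648 | 0.511 / 0.495 |
| Set 1: clinic fixed effects, participant-level SE | 0.954 / 0.951 | 0.729 / 0.739 | 0.467 / 0.452 |
| Set 2: clinic cluster, Mancl-DeRouen, t(9) | 0.950 / 0.959 | 0.59 / 0.61 | 0.543 / 0.526 |
| Set 2: clinic fixed effects, participant-level SE | 0.948 / 0.952 | 0.735 / 0.762 | 0.466 / 0.451 |
| Set 2: clinic cluster, uncorrected, normal | 0.887 / 0.895 | – | – |

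Width ratios: 0.511/0.467 = 1.09 and 0.543/0.466 = 1.17. Power differences at ICC 0.025: 0.729 − 0.642 = 0.087 and 0.735 − 0.59 = 0.145; further runs gave 0.74 to 0.75 against 0.59, or 15 to 16 points.

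**5. Both primary models.** Simulating the negative-binomial offset model and the two-time-point medication model (300 to 400 runs, no effect, log link with Poisson working variance for medications), the Mancl-DeRouen t(9) half-width against the stratified participant-level one was 0.207 versus 0.167 for care gaps (ratio 1.24) and 0.255 versus 0.214 for medications (1.19). Across scenarios with a constant effect it was 18% to 25% wider.

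**6. If the effect varies by clinic.** With an assumed SD of the log relative rate of 0.15, participant-level intervals covered the average effect in a wider population of clinics about 0.88 to 0.94 of the time. The Mancl-DeRouen t(9) interval held 0.945 for care gaps and 0.960 for medications (independence working correlation, ICC 0.024).

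**The case against.** The strongest reply has four parts.

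- *Clinic is accounted for.* With both arms in every clinic, the contrast is already essentially within-clinic, and the clinic-level sandwich credits that balance. This stands. A reader might infer that omitting the clinic term loses precision in the estimate, or that the analysis pays the design effect of a cluster-randomized trial. Neither follows: the estimator's SD is almost the same either way, and the 80% inflation does not carry over.
- *The wide interval is not the plan's.* No correction or t(9) is specified. An uncorrected sandwich with normal critical values is equally permitted and gave a narrower interval than the proposed fix (median width 0.419 versus 0.458, power 0.774 versus 0.743). This is true, but its coverage was 0.907, so the shorter interval is bought with under-coverage. Under either reading the plan does worse for these ten clinics.
- *Clinic-level inference is a legitimate target.* In a pragmatic trial one may wish to generalize beyond the participating clinics, and participant-level intervals then under-cover if effects vary. This stands, and is why the target should be stated and both analyses shown. The document names no wider target.
- *The change is post hoc.* The study ended in January 2025 and the methods are written in the past tense. Replacing the analysis with one that yields narrower intervals invites suspicion. This stands as a condition on reporting.

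**Conclusion.** The point holds as a mismatch between the unit randomized and the unit used for variance. Its cost is in the intervals and p-values of both primary outcomes, not in the point estimates. An uncorrected clinic-level analysis covers about 0.89 to 0.91, with type I error about 0.10. A corrected t(9) analysis is about nominal but roughly 10% to 25% wider, with about 9 to 16 points less power, than a stratified participant-level analysis with about 95% coverage.

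That last coverage depends on a constant effect across clinics. The sizes rest on assumed N, clinic sizes and event rates, and the width penalty depends on the correction chosen. The ratio of 1.154 needs no assumed rates, though 9 degrees of freedom is a convention. It would go too far to say that the reported p-values are anti-conservative: the document does not say how the standard errors were computed. The change is worth making, because it uses data already held and keeps the relative-rate scale.

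**What to change.** Make both changes together; adding clinic while still clustering on clinic gains nothing.

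1. Add clinic as a fixed stratum effect (nine indicators) to every between-arm model.
2. Base the robust variance on the participant: participant-level robust errors for cross-sectional outcomes, and clustering on participant for outcomes measured at both time points. If the log-binomial model does not converge, use a Poisson working variance with the log link.
3. State that this inference is to the ten participating clinics. Report alongside it the clinic-clustered GEE with a named small-sample correction and t(9), for readers interested in a wider population of clinics.
4. State the working correlation, standard-error type and degrees of freedom of the analysis described.
5. Because the trial is complete, label the re-analysis as a change and show it beside the planned analysis, whichever way the results differ.

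The cost is revised SAP wording and a re-run. No new data are needed. The model spends nine degrees of freedom on clinic, and its conclusion is limited to these clinics.

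### The longitudinal GEE text names only the clinic as correlation level, so use of a participant's own Week 0 value is unspecified; the missing-data power example and the geometric-mean label also need correcting

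*Combined protocol and SAP*

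**What the plan says.** All passages are in the combined protocol and SAP, mostly under Analysis Methods.

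- **Correlation.** All outcomes are analysed by GEE "while accounting for correlated outcomes within study clinics". For longitudinal outcomes the fixed effects are time and time-by-arm, and the models "nest correlated outcomes within study clinics". The baseline constraint is repeated for the medications co-primary, "which estimates equal rates by arm at baseline". No participant level, working correlation or variance estimator is stated.
- **Equivalence and power.** "The cLDA model is equivalent to the ANCOVA model when no data are missing". The text adds that participants with some missing values, with follow-up as its example, "contribute to the cLDA model but not the ANCOVA model", and that this raises relative power.
- **Where data can be missing.** Dropout is described as "affecting Week-16 survey outcomes only". Under Recruitment, enrollment, and randomization: "After obtaining baseline survey measurements, the RA activated a lookup feature to reveal the" participant's assignment. Medications are scored from health records at both times, Week 16 "using EHR data from the 16-week intervention period".
- **Label.** SGRQ and PACIC are given a log link and a negative binomial distribution, and the estimates are called geometric means. The SGRQ paragraph says that z is modelled but gives the distribution of y. No log transformation is described.

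**The concern.** The mean model has three parameters for three cells: common Week 0, UC Week 16 and HC Week 16. No baseline covariate is included. A participant's own Week 0 value can therefore inform the arm effect only through the within-participant correlation, which is the element left unstated.

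At stake is the precision of one co-primary outcome and of the longitudinal secondary outcomes, and their protection against chance baseline imbalance. The reader is also told that the model gains power from dropouts, and is told that the means are geometric. Neither statement fits the models described.

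**Working it through.** The plan gives no sample size calculation, SD, within-participant correlation or dropout rate, so there is no stated figure to reproduce.

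**Inputs.** From the documents: ten clinics; 1:1 randomization within clinic; 165 coached patients, doubled to 330 on the assumption of an equal UC arm. Assumed: r (or phi for a binary outcome) of 0.3 to 0.7; SGRQ-like scores with mean 45 and SD 18 to 20; clinic ICC of 0.02 to 0.025; two-sided alpha of 0.05. An ICC of 0.025 with 33 participants per clinic gives 1 + 32 × 0.025 = 1.80, consistent with the nearly 80% inflation mentioned in the recruitment section.

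**1. What a clinic-only fit estimates.** With an independence working correlation, the Week 16 log ratio equalled the crude log ratio of means to within 5e-16. With an exchangeable clinic correlation the empirical SD was the same, 0.0444 against 0.0444 (400 simulated trials, r = 0.7). A participant-level fit gave 0.0311.

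**2. Size of the loss if clustering was clinic-only.** Variance relative to a participant-level fit is 1/(1 − r²). Simulated values are squared SD ratios from 1,500 data sets per r.

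| r | 1/(1 − r²) | Simulated, SGRQ-like |
|---|---|---|
| 0.3 | 1/0.91 = 1.10 | (0.0495/0.0477)² = 1.08 |
| 0.5 | 1/0.75 = 1.33 | (0.0493/0.0429)² = 1.32 |
| 0.7 | 1/0.51 = 1.96 | (0.0485/0.0344)² = 1.99 |

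For a binary medications-type outcome at phi of about 0.49, the simulated ratio ran from (0.0885/0.0790)² = 1.25 to (0.0801/0.0685)² = 1.37 across assumed rates; the scenario giving 1.37 gave 1.30 with another seed.

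At r = 0.5, confidence intervals are √1.33 = 1.15 times as wide, and 330 participants carry the information of 330 × 0.75 ≈ 248. An effect with 80.0% power under clinic-only correlation would have 83.6%, 89.9% and 97.5% power at r = 0.3, 0.5 and 0.7 under a participant-level fit.

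**3. Chance imbalance, same condition.** At phi of about 0.49, the 95th percentile of the absolute log-RR difference between the two fits was 0.075 to 0.133. Since exp(0.075) = 1.08 and exp(0.133) = 1.14, one data set in twenty would show medications RRs differing by more than 8 to 14%.

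**4. Power example.** In the linear model the likelihood factors into Week 0, and Week 16 given Week 0 and arm. Baseline-only participants enter only the first factor. With 140 completers per arm, unit variance and r = 0.5:

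- ANCOVA: 2 × 0.75/140 = 0.010714.
- cLDA on the same completers: 0.010714.
- cLDA plus 25 baseline-only participants per arm: 0.010714.
- cLDA plus 25 Week-16-only participants per arm: 0.009449.

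Under the log link, baseline-only participants reduce the variance by 0 to 0.18% (r of 0.5 to 0.7, mean ratio 1.0 to 0.8). The gain comes from Week-16-only participants: with a fraction f lacking Week 0 it is 1 + [f/(1 − f)](1 − r²), which is 1.08 at f = 0.1 and r = 0.5.

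**5. Equivalence.** It is exact for linear models with participant-level covariance. With complete data, participant-level log-link cLDA and log-link ANCOVA differed by 0.006 to 0.008 on average in the SGRQ-like log ratio. Clinic-only against ANCOVA differed by 0.020 to 0.027 (r of 0.5 to 0.7).

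**6. Label.** A log-link negative binomial model fitted to two groups of raw scores returned 45.22 and 37.21. These equal the arithmetic means; the geometric means were 38.63 and 24.57. The fitted ratio was 0.823, equal to the arithmetic ratio, against a geometric ratio of 0.636.

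**The case against.** **The harmless reading of nesting.** The general sentence on GEE already covers clinic correlation. If the longitudinal sentence means clinic-only as well, it is redundant; read as participants' repeated outcomes nested in clinics, it adds something. The equivalence sentence also presupposes participant-level correlation. This stands: a reader might infer that the reported analysis ignored baseline, or is biased, but the documents show neither. They leave the level unstated, and a clinic-only fit would cost precision rather than consistency.

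**The power clause fails only in its example.** A reader might infer that cLDA gains nothing from incomplete data, or that no participant could have Week 16 without Week 0 data. Neither follows. Taking the baseline survey before the arm was revealed does not make every item scorable. Inhaler adherence concerns controller medications, so a participant without one at baseline might have no defined Week 0 value; the scoring is not described. Baseline-only participants also sharpen the arm-specific Week 16 means. With 30% missing, that variance is proportional to (1 − r²)/0.7 + r²/2 with them and (1 − r²)/0.7 + r²/1.4 without: 1.196 against 1.250 at r = 0.5 (4% lower) and 0.974 against 1.079 at r = 0.7 (10% lower). This stands, and it rules out simply deleting the clause.

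**The label may be right and the model description wrong.** Geometric means are mentioned twice in Analysis Methods, and the z/y mismatch leaves a transformed score possible. A reader might infer that the results must be relabelled as arithmetic. That holds only if the raw score was modelled.

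**Conclusion.** The concern holds as a specification gap with a conditional cost. Only the clinic is named, and a literal clinic-only fit would largely waste the baseline measurements and break the claimed ANCOVA equivalence. Its variance would be about 1.1 to 2 times that of a participant-level fit for r of 0.3 to 0.7, a range assumed because the documents give no correlation. If participants within clinics was the structure used, the loss is nil and only the wording is incomplete.

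Two statements are wrong as written whichever structure was used. Participants missing only follow-up do not increase power for the Week 16 arm contrast; the gain is exactly zero in the linear model and negligible under the log link. The geometric-mean label does not match a log-link negative binomial model on an untransformed score. Exact ANCOVA equivalence is also overstated for the log-link models specified.

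**What to change.** 1. State the GEE subject, working correlation and variance estimator for the longitudinal outcomes. Specify within-participant Week 0 to Week 16 correlation, or adjustment for own baseline, while accounting for clinic. With ten clinics, the variance estimator needs to be explicit for the p-values to be judged.
2. If that structure was used, only the text changes. If clinic-only was used, keep it as the reported analysis and add the participant-level fit for medications, SGRQ and PACIC as a sensitivity analysis labelled post hoc.
3. Replace the follow-up example with participants who have Week 16 but no Week 0 data, if any exist; otherwise drop the claimed gain. Limit exact ANCOVA equivalence to linear models with participant-level covariance.
4. State whether the raw or a log-transformed score was modelled, and use one symbol. If raw, label SGRQ and PACIC results as arithmetic means and their ratio. If log-transformed, describe that model and the handling of an SGRQ score of 0.

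The cost is a few sentences, plus a small re-analysis of existing data only if clustering was clinic-only. No patient contact or data collection is needed. The study ended in January 2025 and the document is dated September 30, 2025, so any re-analysis is post hoc if results are known.
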